### 9.5 Extent of Exposure (Product Consumption)

All subjects in the P4M3 (both CA35 and CM35) and CIG arms will be permitted *ad libitum* use of the respective products, while the SA arm will abstain from CIG smoking.

This data will be summarised for the FAS, PPS, and SAF, as well as stratified using the factors described in section 9.1.1, as follows:

For the CIG group, the following parameters will be summarized:

- Number of cigarette butts and percent change from baseline for Day 1, 2, 3, 4, 5,
- Average number of cigarette butts per day (computed using the sum of all cigarette butts collected over Days 1-5 divided by the number of days spent by the subject in the exposure period) and percent change from baseline,

#### Confidentiality Statement

---

Data and information contained in this document are considered to constitute trade secrets and confidential commercial information, and the legal protections provided to such trade secrets and confidential information are hereby claimed under the provisions of applicable law. No part of this document may be publicly disclosed without the written consent of Philip Morris Products S.A.

---

- Total cigarette butts over 5 days.

For the P4M3 CA35 and P4M3 CM35 groups, the following parameters will be summarized:

- Number of cartridges for Day 1, 2, 3, 4, 5,
- Average number of cartridges used per day (computed using the sum of all cartridges used over Days 1-5 and divided by the number of days spent by the subject in the exposure period),
- Total number of cartridges used over 5 days.,
- Weight of e-liquid used per day for Day 1, 2, 3, 4, 5 (where weight is calculated as post-product use cartridge weight subtracted from pre-product use cartridge weight in mg),
- Average weight of e-liquid used per day (computed using the sum of all weights of e-liquid used over Days 1-5 and divided by the number of days spent by the subject in the exposure period),
- Total weight of e-liquid used over 5 days.

All exposure data will also be listed.

## 9.6 Planned Statistical Analyses

### 9.6.1 Primary Objective: Primary Estimand Analysis

The primary objective of the study is to demonstrate the reduction of BoExp to selected HPHC in smokers switching from CIG to P4M3 (combined CA35 and CM35 arms) compared to continuing CIG smoking for 5 days.

#### 9.6.1.1 Primary Estimand

The primary estimand of the primary objective is defined by the following components:

- Product Use Under Evaluation: This corresponds to the study arms (CIG, P4M3 CA35, P4M3 CM35, or SA) randomly allocated to subjects and for which they have fulfilled key compliance criteria of the protocol, i.e., without major protocol deviations that impact the evaluability of the primary objective (as defined by the PPS).
- Target Population: This is the population of adult smokers who satisfy all eligibility criteria.
- Variables of Interest: 3-HPMA, 2CyEMA, total NNAL (all expressed as concentration adjusted for creatinine in 24-hour urine), and COHb (expressed as % of saturation of hemoglobin).

#### Confidentiality Statement

---

Data and information contained in this document are considered to constitute trade secrets and confidential commercial information, and the legal protections provided to such trade secrets and confidential information are hereby claimed under the provisions of applicable law. No part of this document may be publicly disclosed without the written consent of Philip Morris Products S.A.

---

- Intercurrent Events (ICEs):
  - Non-adherences to the randomization arm: these ICEs are out of scope of this primary estimand, and related subjects will be excluded from this analysis.
  - Study discontinuation and death: data related to subjects who discontinued or died during the exposure period will be included only if they were adherent until the time of discontinuation/death.
  - Subjects that test COVID-19 positive during the study: subjects will be included only until the time of the diagnosis or vaccination. Data collected after or at the date of the COVID-19 positive test will be reported as missing.
  - Changes in comorbidities: subjects with comorbidities or worsening of an existing comorbidity will be included as this change may be linked to the reduction or modification of their CIG consumption.
- Population-Level Summary Statistic: geometric mean ratios between P4M3 (CA35 and CM35 combined) and CIG of the BoExp under consideration at Day 5.

### 9.6.1.2 Main Analysis

The primary analysis will be a mixed model for repeated measures (MMRM) conducted with the PPS. An unstructured matrix will be used to model the variance-covariance structure within subjects. If this model fails to converge, then the following variance-covariance matrices will be used (in order) until one converges: Heterogeneous Toeplitz, Heterogeneous First Order Autoregressive, Heterogeneous Compound Symmetry, Variance Components, Compound Symmetry, and finally no repeated statement.

The model for the endpoint expressed on the log-scale will adjust for the endpoint value at baseline (log-scale), Day, randomization arm, and its interaction with Day, and sex. The model described above will be implemented in the SAS® language as:

```
PROC MIXED data=dataset method=reml nobound;
  class Arm Day Subject Sex;
  model Log(Endpoint) = Log(Baseline) Day Arm Arm*Day
    Sex / ddfm=kenwardroger2 solution;
  repeated Day / subject=Subject(Arm) type=un rcorr;
  lsmeans Arm*Day / pdiff cl;
  lsmestimate 'Contrast P4M3 (CA35 and CM35 combined) vs. CIG' exact syntax to be
adjusteddepending on the coding of class variables / cl upper alpha=0.025;
  lsmestimate 'Contrast P4M3 CA35 alone vs. CIG' exact syntax to be adjusted depending
on the coding of class variables / cl upper alpha=0.025;
  lsmestimate 'Contrast P4M3 CM35 alone vs. CIG' exact syntax to be adjusted depending
on the coding of class variables / cl upper alpha=0.025;
RUN;
```

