12.5.1.3 Missing Data Strategy

In this analysis, some missing data might occur because of ICEs or because of missing samples, laboratory measurements errors, etc. The main analysis model (see section 12.5.1.4) assumes that subjects with missing data would have outcome data like

Confidentiality Statement

Data and information contained in this document are considered to constitute trade secrets and confidential commercial information, and the legal protections provided to such trade secrets and confidential information are hereby claimed under the provisions of applicable law. No part of this document may be publicly disclosed without the written consent of Philip Morris Products S.A

those in similar subjects in the same group. This type of assumption is referred to as Missing at Random (MAR). This assumption is aligned with the definition of the primary estimand.

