#### 9.6.4.6 Exploratory Objective 6: CYP1A2 Enzymatic Activity

In this study, the CYP1A2 enzymatic activity will be calculated using the molar ratio of PX and CAF, as described in section 5.5.

The statistical analyses described in 9.6.1 and 9.6.2 will be repeated using the CYP1A2 enzymatic activity expressed as % as endpoint (no logarithmic transformation will be performed). Because CYP1A2 enzymatic activity will only be measured at baseline and Day 5, the REPEATED statement in the model becomes irrelevant and will not be included. Similarly, the terms Day and Arm\*Day in the MODEL statement will be removed and the LSMEANS statement will use Arm instead of Arm\*Day.

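### The covariance fallback list puts Variance Components before Compound Symmetry, so Compound Symmetry is unreachable and the last usable fallback ignores Days 1–4 when Day 5 is missing

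*SAP*

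**What the plan says.** The confirmatory analysis is a mixed model for repeated measures on the log scale, fitted to each biomarker over Days 1–5. The one-sided 2.5% test is the between-arm contrast at Day 5 (SAP 9.6.1.2; Protocol 12.5.1.4 and 12.5.1.4.1).

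- Starting point: "An unstructured matrix will be used to model the variance-covariance structure within subjects".
- Rule on failure: "the following variance-covariance matrices will be used (in order) until one converges".
- Order: Heterogeneous Toeplitz, Heterogeneous AR(1), Heterogeneous CS, then "Variance Components, Compound Symmetry, and finally no repeated statement". The Protocol gives the same order.
- Code: "repeated Day / subject=Subject(Arm) type=un rcorr", with "Sex / ddfm=kenwardroger2 solution" on the model statement. There is no RANDOM statement and no GROUP= option.
- Missing data: Protocol 12.5.1.3 relies on the main model and a missing-at-random assumption. Protocol 12.5.1 keeps data from adherent subjects up to discontinuation and sets values from a positive COVID test onward to missing. SAP section 6 expects up to 15% missing values.
- Multiplicity: four primary and four key secondary biomarkers are modelled separately, and at each level all must be significant (Protocol 12.6.1).

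**The concern.** A fallback list fixes the confirmatory analysis for the case where the preferred model fails. Here it stops doing so at its fifth entry. VC is CS with the correlation set to zero, and it needs no iterative search. Placed ahead of CS, it is always accepted, so the one simple structure that keeps within-subject correlation is never tried.

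That correlation is the only route by which Days 1–4 inform a missing Day 5. Under VC, a subject who leaves on Day 4 because of high values is treated, given arm, baseline and sex, like any other. If such dropout differs between arms, the Day 5 ratio is biased. Because every biomarker must pass, one poorly converging marker is enough to bring the list into play.

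**Working it through.** **1. The plan's own figure.** For the least favourable primary row (3-HPMA, NCT01970982; GMR 52.86%, GCV 39.57%), log SD = √ln(1 + 0.3957²) = 0.381. With 30 vs 15 subjects, SE = 0.381 × √(1/30 + 1/15) = 0.121 and |ln 0.5286| / 0.121 ≈ 5.3. Noncentral-t power is 0.999, and the product over that study's four biomarkers is 0.9990. The simulated 90th percentile of the upper bound is 78.9%, as stated. The power of at least 99% reproduces.

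**2. What VC is under this code.** CS is σ²[(1 − ρ)I + ρJ], and VC is ρ = 0, that is σ²I. Its REML fit is ordinary least squares with σ² = RSS / (N − p), so it converges whenever the fixed effects can be estimated. Omitting the REPEATED statement also gives σ²I. Two of the six fallback steps are therefore dead text.

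**3. Degrees of freedom.** With 15 evaluable subjects in each of four arms, N = 4 × 15 × 5 = 300 and p = 20 arm-by-day cells + baseline + sex = 22, so VC has 278 df. A Day 5-only model has 60 − 6 = 54. The critical value moves from 2.005 to 1.969, about 2%.

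**4. Complete data, no true effect** (6,000 runs; Monte Carlo SE about 0.2 points; one-sided alpha at Day 5). Assumed, not in the documents: log SD 0.35, baseline slope 0.6, exchangeable correlation ρ.

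| Setting | VC | CS | Day 5 ANCOVA |
|---|---|---|---|
| Equal variances, ρ 0.5 / 0.8 / 0.9 | 2.8 / 2.7 / 3.0% | 2.6 / 2.4 / 2.6% | 2.3 / 2.4 / 2.6% |
| Day 5 SD 1.5 × Day 1 SD, ρ 0.7 | 5.1% | 4.7% | 2.4% |
| Day 5 SD 2 × Day 1 SD, ρ 0.7 | 7.7% | 7.1% | 2.6% |
| Day 5 SD 0.67 × Day 1 SD, ρ 0.7 | 1.0% | 0.9% | 2.5% |

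Independence alone costs little. The larger departures come from pooling unequal variances over days. CS shares them, and they go either way.

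**5. Missing Day 5** (1,500 runs; Monte Carlo SE about 0.4 points). Same assumptions. In the value-driven case, P4M3 arms tend to lose high Day 4 values and CIG tends to lose low ones; this is deliberately adverse.

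| Missingness, ρ 0.5 / 0.8 | VC bias in log ratio | VC alpha | CS bias in log ratio | CS alpha |
|---|---|---|---|---|
| About 15%, completely at random | −0.002 / 0.001 | 2.3 / 2.3% | −0.001 / 0.000 | 2.5 / 2.0% |
| About 14%, driven by Day 4 | −0.060 / −0.095 | 6.3 / 10.7% | +0.003 / +0.006 | 2.4 / 2.6% |

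On the ratio scale the VC bias is exp(−0.060) = 0.94 and exp(−0.095) = 0.91.

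**6. When CS is not the true structure.** The data in step 5 were generated under CS, which favours it. A separate simulation used AR(1) correlation 0.7 / 0.9, with dropout before Day 5 in the P4M3 arms only, driven by Day 4 values. Bias was −0.065 / −0.044 under VC and −0.032 / −0.017 under CS; alpha was 10.6 / 12.4% against 7.0 / 6.6%. CS is clearly better than VC but not clean.

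**7. A Day 5 ANCOVA under dropout.** With 36 vs 18 subjects, the P4M3 subjects with the top 15% of Day 2 values removed from Day 3, AR(1) correlation 0.7 / 0.9 extended to baseline, log SD 0.38 and 1,500 runs, the Day 5 ratio was biased by a factor 0.98 / 0.97 for the ANCOVA and 0.99 / 0.99 for VC. The ANCOVA protects the variance but not against value-driven dropout.

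**The case against.** The strongest reply is that this step is remote and its effect modest. Four structures must fail first. In a check outside SAS (60 subjects, 5 days, AR(1) correlation 0.7, 10% monotone dropout), 100 of 100 unstructured fits converged. Planning ratios for the primary biomarkers run from 13% to 53%. This stands, with the limit that well-behaved simulated data say little about a real marker with values set to LLOQ/2.

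Three stronger readings are tempting and should be resisted.

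- A reader might infer that treating five days as independent inflates type I error in general. It does not: the contrast is between arms at one day, and with complete data and equal variances alpha is 2.7–3.0%. Values of 5–8% need Day 5 variability to rise, CS is affected almost equally, and alpha falls to about 1% if variability declines. The documents give no day-level variances.
- A reader might infer that the missing-at-random strategy is lost. It is narrowed. VC remains valid if missingness depends only on arm, day, baseline and sex, and Protocol 12.5.1.3 speaks only of similar subjects in the same group. What goes is protection when missingness depends on earlier post-baseline values.
- A reader might take the CYP1A2 model in SAP 9.6.4.6, where "the terms Day and Arm\*Day in the MODEL statement will be removed", as a ready last resort. CYP1A2 has no post-baseline value before Day 5, so nothing is discarded there. For the biomarkers, Days 1–4 would be.

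**Conclusion.** The ordering defect is certain: it follows from the list, the convergence rule and the code, and it is in both documents. If the fallback reaches VC, the Day 5 ratio and its test are exposed to missingness that depends on earlier post-baseline values, clearly more than under CS (6–11% against about 2.5% where CS is correct; 10.6–12.4% against 6.6–7.0% under AR(1)). These sizes rest on assumed correlations, an assumed log SD and adverse dropout. With values missing completely at random there is no bias and no inflation.

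The chance of reaching VC cannot be estimated from the documents. The planned conclusion is unlikely to change: dividing the worst primary upper bound by the largest simulated bias gives 78.9% / 0.91 ≈ 87%, still below 100%. The case for acting is that confirmatory error control should not rest on a misordered list that costs nothing to correct.

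**What to change.** In SAP 9.6.1.2 and Protocol 12.5.1.4, order the list as Unstructured, Heterogeneous Toeplitz, Heterogeneous AR(1), Heterogeneous CS, Compound Symmetry. Delete Variance Components and the step without a repeated statement.

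Do not put a plain Day 5 ANCOVA in their place. If a last resort after CS is wanted, it should keep a Day 5-specific variance and impute missing Day 5 values from the earlier days. The variance requirement matters because the reorder alone does not repair pooling of unequal variances.

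The cost is a wording change before database lock. Nothing changes for any biomarker whose unstructured model, or one of the three heterogeneous structures, converges.

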12.5.1.4 Main Analysis

The primary analysis will be conducted in the PP and based on a mixed model for repeated measurements (MMRM). An unstructured matrix will be used to model the variance-covariance structure within subjects. If this model fails to converge, then the following variance-covariance matrix will be used (in order) until one converges: Heterogeneous Toeplitz, Heterogeneous First Order Autoregressive, Heterogeneous Compound Symmetry, Variance Components, Compound Symmetry, and finally no repeated statement.

The model for the endpoint expressed on the log-scale will adjust for the endpoint value at baseline (log-scale), the Day, the randomization study arm and its interaction with Day, and sex.

The model described above will be implemented in the SAS® language as:

```
PROC MIXED data=dataset method=reml nobound;
  class Arm Day Subject Sex;
  model Log(Endpoint) = Log(Baseline) Day Arm Arm*Day
    Sex / ddfm=kenwardroger2 solution;
  repeated Day / subject=Subject(Arm) type=un rcorr;
  lsmeans Arm*Day / pdiff cl;
  lsmestimate 'Contrast P4M3 (CA35 and CM35 combined) vs. CIG' exact syntax to be adjusted
  depending on the coding of class variables / cl upper alpha=0.025;
  lsmestimate 'Contrast P4M3 CA35 alone vs. CIG' exact syntax to be adjusted depending
  on the coding of class variables / cl upper alpha=0.025;
  lsmestimate 'Contrast P4M3 CM35 alone vs. CIG' exact syntax to be adjusted depending
  on the coding of class variables / cl upper alpha=0.025;
RUN;
```

LS-means per randomization study arm and day will be obtained (on the log-scale), as well as pairwise differences between arms per day, together with their 95%-confidence intervals and (unadjusted) p-values. Exponentiation of these quantities will lead to the geometric LS-means per randomization study arm and (geometric) ratios between arms with their associated 95%-confidence intervals.

The exponentiation of the 'lsmestimate' statement above entitled 'Contrast P4M3 (CA35 and CM35 combined) vs. CIG' will allow contrasting the 2 P4M3 Gen 2.0 CA35 and CM35 study arms combined against the CIG arm and will be used to assess the primary study hypothesis (see section 12.5.1.4.1). Similarly, the exponentiation of the 2 subsequent 'lsmestimate' statements will be used to assess the key secondary objectives 2 and 4 if the procedure of fixed sequence testing allows it (see section 12.6.1).

Confidentiality Statement

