12.5.1.4.1 Success Criteria

The primary study hypothesis is about demonstrating the reduction of the four BoExp to selected HPHC given in [Table 4](#) in smokers switching from CIG to P4M3 (CA35 and CM35 combined) for 5 days as compared to those who continue smoking CIG. For each individual BoExp, this will be evaluated using the 1-sided statistical test with a type I error level of 2.5% given by the 'lsestimate' statement 'Contrast P4M3 (CA35 and CM35 combined) vs. CIG' of the model described in section [12.5.1.4](#).

The study will be declared successful if the ratio of the geometric means between P4M3 (CA35 and CM35 combined) over CIG is statistically lower than 1 at Day 5 for all four BoExp tested in the primary objective given in [Table 4](#).

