### 3.5 Study Hypotheses and Evaluation Criteria

#### 3.5.1 Hypotheses

The primary study hypothesis is that there is a reduction in all BoExp to the selected HPHC that are examined for the primary objective, in subjects switching to P4M3 (subjects of CA35 and CM35 pooled together) compared to subjects continuing CIG.

Specifically, the primary hypothesis ( $H_1$ ) is:

- The geometric mean ratio (P4M3/CIG) of 3-HPMA at Day 5 is less than 1 and
- The geometric mean ratio (P4M3/CIG) of 2-CyEMA at Day 5 is less than 1 and
- The geometric mean ratio (P4M3/CIG) of total NNAL at Day 5 is less than 1 and
- The geometric mean ratio (P4M3/CIG) of COHb at Day 5 is less than 1

For the key secondary objective, the hypotheses ( $H_x$ ) are defined sequentially in this order:

$H_2$ :

- The geometric mean ratio (P4M3/CIG) of S-PMA at Day 5 is less than 1 and
- The geometric mean ratio (P4M3/CIG) of 3-HMPMA at Day 5 is less than 1 and
- The geometric mean ratio (P4M3/CIG) of total NNN at Day 5 is less than 1 and
- The geometric mean ratio (P4M3/CIG) of 3-OH-B[a]P at Day 5 is less than 1

$H_3$ :

- The geometric mean ratio (CA35/CIG) of 3-HPMA at Day 5 is less than 1 and

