## 6 SAMPLE SIZE JUSTIFICATION

In this study, 72 subjects are randomized as follows:

- 36 in combined P4M3 arms (18 in CA35 and 18 in CM35),
- 18 in CIG arm,
- 18 in SA arm.

Based on four previous similar studies conducted by PMI on the tobacco heating system (another alternative product to CIG developed by PMI which is likely to be less risky than cigarette; ClinicalTrials.gov identifiers are NCT01970995, NCT01989156, NCT01959932, and NCT01970982, respectively), Table 8 contains estimates of geometric mean ratios (GMR) and associated coefficients of variations (GCV) for the (adjusted) contrast of a tobacco heating system against CIG. The effect of P4M3 is expected to be similar (or better) on the BoExp selected in this study compared to this tobacco heating system. In addition, based on these studies, up to 15% of missing values may be expected for various reasons (e.g., withdrawals, mis-randomization, etc.).

Using the statistics displayed in Table 8, the sample size planned for this study accounting for 15% of missing values (resulting in 30 and 15 subjects in P4M3 combined and CIG arms, respectively), and a one-sided two-sample t-test (on the log-scale) with 2.5% type I error probability, the estimated power for each BoExp is displayed in Table 8. By multiplying the power for each individual BoExp over the four to be tested in the primary hypothesis (per study), a global estimate of power is also obtained.

Note that 10,000 simulations of one-sided two-sample t-test were also conducted to determine the 90 percentiles of the (upper) half-width of the 97.5%-confidence interval (CI) of the ratio between P4M3 and CIG, as well as the 90 percentiles of the upper bounds of these CIs. These are also displayed in Table 8. These provide indications on the expected precision on the estimates of the ratios.

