### 9.1.7 Multiple Comparison/Multiplicity

Overall family-wise type I error will be preserved at the  $\alpha$ -level of 2.5% (1-sided tests will be conducted for the primary and key secondary study hypotheses). This will be done by using a fixed sequence of testing: primary objective  $\rightarrow$  1st key secondary objective  $\rightarrow$  2nd key secondary objective  $\rightarrow$  3rd key secondary objective  $\rightarrow$  4th key secondary objective  $\rightarrow$  5th key secondary objective. All objectives will be tested sequentially in a given order at the 2.5% type I error level until one of the objectives is rejected in which case all subsequent testing will be exploratory 2-sided tests at an  $\alpha$ -level of 5%, and the associated 2-sided 95% confidence interval will be reported.

The primary study hypothesis will be tested 1-sided with a type I error  $\alpha$ -level of 2.5%. The associated 1-sided 97.5% confidence interval will be provided. This will be applied to all BoExps of [Table 1](#) that are part of the primary study hypothesis. Subsequent analyses of objectives will only proceed if this hypothesis is not rejected.

If the primary study hypothesis is not rejected, the same  $\alpha$ -level of 2.5% will be used for the 1st key secondary hypothesis and the associated 1-sided 97.5% confidence interval will be reported. This will be applied to all BoExps of [Table 2](#) that are part of the 1st key secondary hypothesis. Subsequent analyses will only proceed if the hypothesis is not rejected.

The analysis will proceed in a similar way for the following key secondary objectives.

For all the exploratory objectives, the statistical tests will be 2-sided with an  $\alpha$ -level of 5%. Associated 2-sided 95% confidence intervals will be provided.

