### Confidentiality Statement

Data and information contained in this document are considered to constitute trade secrets and confidential commercial information, and the legal protections provided to such trade secrets and confidential information are hereby claimed under the provisions of applicable law. No part of this document may be publicly disclosed without the written consent of Philip Morris Products S.A

LS-means per randomization arm and day will be obtained (on the log-scale), as well as pairwise differences between arms per day, together with their 95%-confidence intervals and (unadjusted) p-values. Exponentiation of these quantities will lead to the geometric LS-means per randomization arm and (geometric) ratios between arms with their associated 95%-confidence intervals.

The exponentiation of the 'lsmestimate' statement above entitled 'Contrast P4M3 (CA35 and CM35 combined) vs. CIG' will allow contrasting the two P4M3 Gen 2.0 CA35 and CM35 study arms combined against the CIG arm and will be used to assess the primary study hypotheses. Similarly, the exponentiation of the two subsequent 'lsmestimate' statements will be used to assess the key secondary objectives 2 and 4 if the procedure of fixed sequence testing allows it.

For each individual BoExp in the Primary Analysis, the hypothesis will be evaluated using the 1-sided statistical test with a type I error level of 2.5% given by the 'lsmestimate' statement 'Contrast P4M3 (CA35 and CM35 combined) vs. CIG' of the model described in this section.

The study will be declared successful if the ratio of the geometric means between P4M3 (CA35 and CM35 combined) over CIG is statistically lower than 1 at Day 5 for all four Primary BoExp.

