### 9.6.1.3 Supportive/Sensitivity Analyses

The model described in section 9.6.1.2 will be used to contrast all randomization arms at Days 1, 2, 3, 4, and 5. Pairwise comparisons at Days 1, 2, 3, 4, and 5 will be reported, together with their unadjusted p-values and 95%-confidence interval:

- P4M3 (CA35 and CM35 combined) vs. CIG
- SA vs. CIG
- P4M3 (CA35 and CM35 combined) vs. SA
- P4M3 CA35 vs. CIG
- P4M3 CM35 vs. CIG
- P4M3 CA35 vs. SA
- P4M3 CM35 vs. SA
- P4M3 CA35 vs. P4M3 CM35

Contrasts P4M3 CA35 vs. CIG and P4M3 CM35 vs. CIG will also be estimated one-sided with a type I error level of 2.5% through the additional 'lsmestimate' statements. These contrasts will be used to assess the key secondary objectives 2 and 4 if the procedure of fixed sequence testing (see section 9.6.3) allows.

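### The three confirmatory LSMESTIMATE lines specify `upper`, the wrong tail for a P4M3 minus CIG contrast that must show a ratio below 1

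*SAP*

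**What the plan says.** SAP 9.6.1.2 prints a PROC MIXED program with three LSMESTIMATE statements: combined P4M3 against CIG, CA35 against CIG, and CM35 against CIG. The first ends "adjusteddepending on the coding of class variables / cl upper alpha=0.025" and the other two carry the same options. Protocol 12.5.1.4 prints the same program ("depending on the coding of class variables / cl upper alpha=0.025"). The coefficients are left to the programmer, but `upper` stands after the slash as a fixed option.

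The text makes this code the decision rule. Protocol 12.5.1.4.1 says that for each biomarker "this will be evaluated using the 1-sided statistical test with a type I error level of 2.5% given by the" LSMESTIMATE statement for the combined contrast. SAP 9.6.1.2 says the same, adds that the contrast is exponentiated to assess the hypothesis, and declares success if the ratio of P4M3 over CIG "is statistically lower than 1 at Day 5 for all four Primary BoExp".

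SAP 3.5.1 states every hypothesis in that direction, for example "The geometric mean ratio (P4M3/CIG) of 3-HPMA at Day 5 is less than 1 and", with the corresponding ratios to CIG for the other biomarkers and for each variant.

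On intervals, SAP 9.1.7 says "The associated 1-sided 97.5% confidence interval will be provided" without naming the bound. SAP 6 reports upper bounds in its planning simulations ("as well as the 90 percentiles of the upper bounds of these CIs"). SAP 9.6.1.3 also plans two-sided intervals: "Pairwise comparisons at Days 1, 2, 3, 4, and 5 will be reported, together with their unadjusted p-values and 95%-confidence interval".

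**The concern.** A ratio of P4M3 over CIG below 1 is a negative P4M3 minus CIG contrast on the log scale. Demonstrating it needs the lower-tail p-value and an upper confidence limit. In ordinary SAS usage `upper` gives the opposite of both: the probability of a larger t value, and an interval with a lower limit only.

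The three lines carry the whole confirmatory sequence. The first serves the primary objective. The second and third serve key secondary objectives 2 and 4. The same model, rerun on the second set of biomarkers, serves objectives 1, 3 and 5. Run as written with P4M3 minus CIG, the program would print p-values near 1 next to two-sided 95% intervals lying wholly below 1.

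Timing is a lesser point. Under SAP 4.6.2, the statisticians' blinding to biomarker data ends after SAP finalization. A mismatch found later would have to be corrected with the data open. The written hypotheses already fix the direction, so this would be a correction and not a free choice, but it is better made beforehand.

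**Working it through.** **Assumption.** The documents do not define `upper`. It is read here in its ordinary SAS sense: p = P(T > t), with a one-sided interval bounded below. `lower` is the mirror image.

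**Inputs.** GMR and GCV come from Protocol Tables 16 to 19 (64 rows, 16 of them for the primary objective in Table 16). Evaluable numbers are 30 vs 15 for the combined contrast and 15 vs 15 for a single variant (Protocol 12.9.4). Alpha is 2.5% one-sided.

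**Formulas.**
- s = sqrt(ln(1 + GCV²))
- SE = s × sqrt(1/n1 + 1/n2), with df = n1 + n2 − 2
- t = ln(GMR)/SE
- one-sided 97.5% limits = GMR × exp(∓ t(0.975, df) × SE)

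**Reproducing the plan's figures.** With the lower tail, power exceeds 99% in all 16 primary rows, as stated. Simulated 90th percentiles of the upper bound agree with Protocol Table 16 to within about 0.2 points, for example 78.9 against 78.9 and 25.4 against 25.4. With the upper tail on the same contrast there were no rejections in 200,000 runs for any of these rows. The planning therefore used the lower tail.

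**Weakest primary row** (3-HPMA, NCT01970982, GMR 52.86%, GCV 39.57%, 30 vs 15):
- s = sqrt(ln(1 + 0.3957²)) = 0.381
- SE = 0.381 × sqrt(1/30 + 1/15) = 0.1206, df = 43
- t = ln(0.5286)/0.1206 = −0.6375/0.1206 = −5.29

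| | `upper` | `lower` |
|---|---|---|
| p | 0.999998 | 2.0e-6 |
| one-sided 97.5% limit | lower limit 41.4%, no upper limit | upper limit 67.4% |

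Lower-tail power in this row is 99.93%, against the stated >99%.

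**Weakest of the 64 rows** (same endpoint and study, 15 vs 15, df = 28): SE = 0.381 × sqrt(2/15) = 0.139 and t = −4.58. The upper-tail p is 0.99996, the lower-tail p is 4.4e-5 and the upper limit is 70.3%.

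**Across rows,** with observed values equal to the planning values:
- 16 primary rows: upper-tail p at least 0.999998, lower-tail p at most 2.0e-6, upper limit at most 67.4%.
- All 64 rows: upper-tail p at least 0.99996, lower-tail p at most 4.4e-5, upper limit at most 70.3%.

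**What the three possible readings give.**
1. Coefficients P4M3 minus CIG, as the contrast labels and the success ratio imply: wrong tail, as above.
2. Coefficients CIG minus P4M3: right tail, p = 2.0e-6. But the exponentiated estimate is 1/0.5286 = 189% with lower limit 1/0.674 = 148%. That is CIG over P4M3, not the ratio in the success rule.
3. `upper` intended to mean the upper confidence limit, as in the planning tables: plausible, but stated nowhere, and not what the option does in ordinary usage.

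None of the three makes the printed code and the prose agree.

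**The case against.** The strongest reply is that the code is a template. The coefficients are unwritten, so a programmer must complete each line and would set sign and tail together. The direction is already fixed in SAP 3.5.1 and in the success rule, the planned two-sided 95% interval recovers the decision, and a p-value near 1 beside an interval wholly below 1 could not be missed. The meaning of `upper` also comes from general knowledge of the software, not from the documents.

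Much of this stands. The prose rule is correct, no false success would follow, and the dependence on SAS usage is a real condition. The argument also weakens the timing point, because aligning an option with a written hypothesis is not a new choice of test.

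It does not remove the defect. `upper` lies outside the part left for completion, and both documents say that the test is the one this statement gives. To say that a programmer would notice, or that another interval supplies the answer, concedes that the printed line must change.

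**Conclusion.** The point holds and should be fixed. Under ordinary SAS usage and with P4M3 minus CIG, the code on all three confirmatory lines tests the wrong tail and omits the limit needed to show a reduction. At the planning values, every confirmatory p-value would be at least 0.99996 where the intended test gives at most 4.4e-5. With the sign reversed, the tail is right but the reported ratio is inverted.

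The p-values rest on the two-sample t approximation used for planning and on results equal to the planning values; the direction of the mismatch needs neither. Sample size, alpha, stated power and the prose success rule are unaffected. The consequence is a visible contradiction in the confirmatory output, not a wrong claim of benefit.

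**What to change.** In SAP 9.6.1.2:
- Replace `upper` with `lower` in all three LSMESTIMATE statements.
- State that the coefficients are P4M3 (combined, CA35 or CM35) minus CIG at Day 5.
- State that success requires the upper one-sided 97.5% limit of the exponentiated contrast to be below 1, and that this limit equals the upper limit of the two-sided 95% interval.

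Record the departure from the Protocol 12.5.1.4 code in SAP section 7, or align that code as well.

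The cost is three option words, two sentences and one line in section 7. Protocol 12.1 allows changes to the statistical methods to be documented in the SAP and study report, so a SAP revision may suffice; SAP 2.1 shows that one formula has already been corrected this way. If the protocol code is also edited, Protocol 1.1 requires the amendment to go to the ethics committee. Data collection, sample size and participants are not affected.
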